The inclusion of female subjects of childbearing potential requires using at least an acceptable effective contraceptive measure. They must have a negative serum pregnancy test at Screening and a negative pregnancy test on the Day 1 visit prior to first dose of drug. Pregnancy tests will be performed every 4 weeks throughout duration of trial up until and including the posttreatment Week 4 visit. In the event of a delayed menstrual period (over one month between menstruations), a pregnancy test must be performed to rule out pregnancy. This is even true for women of childbearing potential with infrequent or irregular periods. They must also agree to one of the following from Screening until 30 days after the last dose of SOF/VEL FDC or SOF/VEL/VOX FDC.

- Complete abstinence from intercourse of reproductive potential. Abstinence is an acceptable method of contraception only when it is in line with the subject's preferred and usual lifestyle.

Or

- Consistent and correct use of 1 of the following methods of birth control listed below, in addition to a male partner who correctly uses a condom from the date of Screening until 30 days after the last dose of SOF/VEL FDC or SOF/VEL/VOX FDC.

Intrauterine device (IUD) with a failure rate of <1% per year

Intrauterine hormone-releasing system (IUS) with a failure rate of <1% per year

Tubal sterilization

Essure micro-insert system (provided confirmation of success 3 months after procedure)

Vasectomy in the male partner (provided that the partner is the sole sexual partner and had confirmation of surgical success 3 months after procedure)

Barrier methods (one female barrier and one male barrier must be used in combination)

- Female barriers: Diaphragm with spermicide or Cervical cap with spermicide

Hormonal methods

- Oral contraceptives (either combined or progesterone only)
- Injectable progesterone
- Implants of levonorgestrel
- Transdermal contraceptive patch
- Contraceptive vaginal ring

Female subjects must also refrain from egg donation and in vitro fertilization during treatment and until at least 30 days after the last dose of SOF/VEL FDC or SOF/VEL/VOX FDC.

3) Contraception Requirements for Male Subjects

During the study, male subjects with female partners of childbearing potential should use condoms until 30 days after the last dose of SOF/VEL FDC or SOF/VEL/VOX FDC when engaging in intercourse of reproductive potential. If their female partner is of childbearing potential (as defined above), their female partner must use 1 of the methods of birth control listed above from the date of Screening until 30 days after the last dose of SOF/VEL FDC or SOF/VEL/VOX FDC.

Male subjects must also refrain from sperm donation during treatment and until at least 30 days after the last dose of SOF/VEL FDC or SOF/VEL/VOX FDC.

4) Unacceptable Birth Control Methods

Birth control methods that are unacceptable include periodic abstinence (e.g., calendar, ovulation, symptothermal, post-ovulation methods), withdrawal (coitus interruptus), spermicides only, and lactational amenorrhea method (LAM). Female condom and male condom should not be used together.

5) Procedures to be Followed in the Event of Pregnancy

Subjects will be instructed to notify the investigator if they become pregnant at any time during the study, or if they become pregnant within 30 days of last study drug dose. Subjects who become pregnant or who suspect that they are pregnant during the study must report the information to the investigator and discontinue study drug immediately. Subjects whose partner has become pregnant or suspects she is pregnant during the study or within 30 days of last study drug dose must report the information to the investigator. Instructions for reporting pregnancy, partner pregnancy, and pregnancy outcome are outlined in Section [7.5](#).

TEAE	treatment-emergent adverse event
TFLs	tables, figures, and listings
TND	target not detected
ULN	upper limit of normal
VEL	Velpatasvir
VOX	Voxilaprevir
WHO	World Health Organization

PHARMACOKINETIC ABBREVIATIONS

AUC_{last}	area under the concentration versus time curve from time zero to the last quantifiable concentration
AUC_{tau}	area under the concentration versus time curve over the dosing interval
CL/F	apparent oral clearance after administration of the drug: $CL/F = Dose/AUC_{inf}$, where “Dose” is the dose of the drug
C_{last}	last observed quantifiable concentration of the drug
C_{max}	maximum observed concentration of drug
C_{min}	minimum observed concentration of drug
C_{tau}	observed drug concentration at the end of the dosing interval
$t_{1/2}$	estimate of the terminal elimination half-life of the drug, calculated by dividing the natural log of 2 by the terminal elimination rate constant (λ_z)
T_{last}	time (observed time point) of C_{last}
T_{max}	time (observed time point) of C_{max}
λ_z	terminal elimination rate constant, estimated by linear regression of the terminal elimination phase of the concentration of drug versus time curve

1. INTRODUCTION

This statistical analysis plan (SAP) describes the statistical analysis methods and data presentations to be used in tables, figures, and listings (TFLs) in the clinical study report (CSR) for Study GS-US-342-5532. This SAP is based on the study protocol amendment 1 dated 04 October 2019 and the electronic case report form (eCRF). The SAP will be finalized before database finalization. Any changes made after the finalization of the SAP will be documented in the CSR.

1.1. Study Objectives

The primary objective of this study is as follows:

- To evaluate the antiviral efficacy of therapy with sofosbuvir/velpatasvir (SOF/VEL) fixed-dose combination (FDC) for 12 weeks and sofosbuvir/velpatasvir/voxilaprevir (SOF/VEL/VOX) FDC for 12 weeks as measured by the proportion of subjects with sustained virologic response 12 weeks after cessation of treatment (SVR12)
- To evaluate the safety and tolerability by review of the accumulated safety data

The secondary objectives of this study are as follows:

- To determine the proportion of subjects who attain SVR at 4 weeks after cessation of treatment (SVR4)
- To evaluate the proportion of subjects with virologic failure
- To evaluate the emergence of viral resistance to SOF, VEL and VOX during treatment and after cessation of treatment

1.2. Study Design

This is a multicenter, open-label study in approximately 80 subjects with chronic HCV infection.

Cohort 1: Approximately 50 subjects with chronic HCV infection, genotype 1 or 2, will be enrolled and treated with SOF/VEL FDC for 12 weeks. Subjects may be treatment-naïve or treatment-experienced with IFN-based treatments.

Cohort 2: Approximately 30 subjects with chronic HCV infection, genotype 1, will be enrolled and treated with SOF/VEL/VOX FDC for 12 weeks. Subjects will be treatment-experienced with NS5A DAA-based treatments.

The total time to complete all study visits is approximately 28 weeks (30 weeks for those requiring an extension to the Screening period):

- 28 days (4 weeks) screening period [up to 42 days (6 weeks) for extenuating circumstances may be granted]
- 12 weeks study treatment period
- 12 weeks posttreatment period

The schedule of assessment is provided as an appendix to the SAP ([Appendix 1](#)).

1.3. Sample Size and Power

For Cohort 1, with approximately 50 subjects enrolled into the study, the 2-sided 95% exact confidence interval (CI) using the binomial distribution (Clopper-Pearson method) of the SVR12 rate will be from 86.3% to 99.5%, assuming the expected SVR12 rate is 95%.

For Cohort 2, with approximately 30 subjects enrolled into the study, the 2-sided 95% exact CI using the binomial distribution (Clopper-Pearson method) of the SVR12 rate will be from 82.8% to 99.9%, assuming the expected SVR12 rate is 95%.

2. TYPE OF PLANNED ANALYSIS

2.1. Data Monitoring Committee

This study does not have a data monitoring committee (DMC).

2.2. Final Analysis

The analysis for the primary efficacy endpoint SVR12 will be conducted when all subjects have completed the posttreatment Week 12 visit or have prematurely discontinued from study. All the safety and efficacy data through the Posttreatment Week 12 visit will be cleaned, finalized and included for the analysis.

3. GENERAL CONSIDERATIONS FOR DATA ANALYSES

Analysis results will be presented using descriptive statistics. For categorical variables, the number and percentage of subjects in each category will be presented; for continuous variables, the number of subjects (n), mean, standard deviation (SD) or standard error (SE), median, first quartile (Q1), third quartile (Q3), minimum, and maximum will be presented.

By-subject listings will be presented for all subjects in the Safety Analysis Set and sorted by unique subject ID number (including site ID and subject ID number), visit date, and time (if applicable). Data collected on log forms, such as AEs, will be presented in chronological order within the subject. The treatment group to which subjects were initially assigned will be used in the listings. Age, sex at birth, race, and ethnicity will be included in the listings, as space permits.

3.1. Analysis Sets

Analysis sets define the subjects to be included in an analysis. Analysis sets and their definitions are provided in this section. The number of subjects eligible for each analysis set will be provided. Subjects who were excluded from each analysis set will be summarized or provided in a by-subject listing with reasons for exclusion.

3.1.1. All Enrolled Analysis Set

All Enrolled Analysis Set includes all subjects who received a study subject identification number in the study after screening.

3.1.2. Full Analysis Set

The Full Analysis Set (FAS) includes all enrolled subjects who took at least 1 dose of study drug and had detectable HCV RNA at baseline. This definition is modified from the definition of FAS specified in the protocol, in order to exclude any subject with undetectable HCV RNA at baseline from efficacy analyses (see Section 6.3). The study drugs in this study include SOF/VEL FDC (Cohort 1) and SOF/VEL/VOX FDC (Cohort 2).

This is the primary analysis set for efficacy analyses.

3.1.3. Safety Analysis Set

The Safety Analysis Set includes all subjects who took at least 1 dose of study drug. This is the primary analysis set for safety analyses.

3.1.4. Pharmacokinetic (PK) Analysis Set

The PK Analysis Set will include all enrolled subjects who took at least 1 dose of study drug and have at least 1 nonmissing concentration value for the corresponding analyte in plasma. This is the primary analysis set for all PK analyses. The analytes of interest may include SOF (and its metabolites GS-566500 and GS-331007), VEL or VOX where applicable. Within the PK Analysis Set, those subjects with PK exposure data successfully derived from the population PK modeling will be included in the analyses related to PK exposure.

CCI

3.2. Subject Grouping

Generally speaking, the efficacy analyses will be performed on FAS by treatment group. Subjects will be grouped according to the HCV genotype (GT1a, GT1b, GT1 total, and GT2) as recorded in the clinical database and overall within each treatment group. The safety analyses will be performed on the Safety Analysis Set by treatment group according to the actual treatment that the subjects received.

For selected analyses, for example, the summary of demographics and baseline characteristics and the primary analysis of the primary endpoint, please refer to the relevant sections for the detailed description of subject grouping.

3.3. Examination of Subject Subgroups

Subject subsets within each genotype will also be explored by baseline characteristics for the primary efficacy endpoint, SVR12. The baseline characteristics include the following:

- age (< 65 years, ≥ 65 years)
- sex (male, female)
- Race
- Ethnicity
- baseline body mass index (BMI) (< 30 kg/m², ≥ 30 kg/m²; < 25 kg/m², ≥ 25 kg/m²)
- cirrhosis (presence, absence)
- IL28B (CC, non-CC; with non-CC further broken down to CT, TT)
- baseline HCV RNA (< 800,000 IU/mL, ≥ 800,000 IU/mL)
- baseline alanine aminotransferase (ALT) (≤ 1.5 × upper limit of normal (ULN), > 1.5 × ULN)
- prior HCV treatment experience (SOF/VEL 12 Weeks: treatment naive, treatment experienced; SOF/VEL/VOX 12 Weeks: treatment experienced)

- prior HCV treatment for treatment experienced subjects (SOF/VEL 12 Weeks: direct acting antiviral [DAA] + pegylated interferon [Peg-IFN] + ribavirin [RBV], Peg-IFN + RBV, Other; SOF/VEL/VOX 12 Weeks: NS5A +/- DAA[s] and Other[s]; with NS5A +/- DAA[s] further broken down to NS5A + NS5B, NS5A + NS3 +/- NS5B, and NS5A +/- Other[s])
- Response to prior HCV treatment (non-responder , relapse/breakthrough, early treatment discontinuation, met a virologic stopping rule not otherwise listed, and unknown) for treatment experienced subjects
- adherence to study regimen (< 80%, ≥ 80%)
- study treatment status (completed study treatment, discontinued study treatment)

3.4. Multiple Comparisons

Adjustments for multiplicity will not be made, because no formal statistical testing will be performed in this study.

3.5. Missing Data and Outliers

3.5.1. Missing Data

In general, missing data will not be imputed unless methods for handling missing data are specified. Exceptions are presented in this document.

For missing last dosing date of study drug, imputation rules are described in Section 3.7.1. The handling of missing or incomplete dates for AE onset is described in Section 7.1.5.2, and for prior and concomitant medications in Section 7.4.

For analyses of categorical HCV RNA data, missing posttreatment HCV RNA data will have the missing data imputed. Missing on-treatment HCV RNA will have missing data imputed up to the time of the last dose (for on-treatment displays). If the study day associated with the last dosing date of any study drug is greater than or equal to the lower bound of a visit window, and the value at the visit is missing, then the value will be imputed. If the study day associated with the last dosing date is less than the lower bound of a visit window then the on-treatment value at that visit will remain missing.

If a HCV RNA data point is missing and is preceded and followed in time by values that are “< lower limit of quantification (LLOQ) target not detected (TND),” then the missing data point will be set to “< LLOQ TND.” If a data point is missing and preceded and followed by values that are “< LLOQ detected,” or preceded by “< LLOQ detected” and followed by “< LLOQ TND,” or preceded by “< LLOQ TND” and followed by “< LLOQ detected,” then the missing value will be set to “< LLOQ detected.” In these situations the data point will be termed a bracketed success; otherwise, the data point will be termed a bracketed failure (ie, ≥ LLOQ detected). If a data point is missing and is not bracketed, the missing data point will also be termed a failure (ie, ≥ LLOQ detected).

For the analyses of continuous HCV RNA efficacy data, when and only when a missing HCV RNA value is imputed as < LLOQ TND or < LLOQ detected according to the imputation rule described above, the corresponding continuous value will be imputed to LLOQ + 1 IU/mL. No other imputation will be performed for continuous HCV RNA data.

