HCV RNA values below the LLOQ for the assay will be set to the lower limit minus 1 for calculation of summary statistics for the actual HCV RNA values and the change from baseline values by study visit. The reported values will be provided in the HCV RNA listing.

For selected analyses of early time point data, HCV RNA data (IU/mL) may be transformed to the logarithmic (base 10) scale (\log_{10} IU/mL).

CCI

CCI

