3.6. Data Handling Conventions and Transformations

By-subject listings will be presented for all subjects in the Safety Analysis Set and sorted by unique subject ID number, visit date, and time (if applicable) unless otherwise specified. Data collected on log forms, such as AEs, will be presented in chronological order within subject.

Age (in years) on the date of the first dose of study drug and sex at birth will be used for analyses and presentation in listings.

If a subject was not dosed with study drug at all, then the date the informed consent was signed will be used instead of the first dose date of study drug.

Non-PK data that are continuous in nature but are less than the lower limit of quantitation (LOQ) or above the upper LOQ will be imputed as follows:

- A value that is 1 unit less than the LOQ will be used to calculate descriptive statistics if the datum is reported in the form of “< x” (where x is considered the LOQ). For example, if the values are reported as < 50 and < 5.0, values of 49 and 4.9, respectively, will be used to calculate summary statistics. An exception to this rule is any value reported as < 1 or < 0.1, etc. For values reported as < 1 or < 0.1, a value of 0.9 or 0.09, respectively, will be used to calculate summary statistics.
- A value that is 1 unit above the LOQ will be used to calculate descriptive statistics if the datum is reported in the form of “> x” (where x is considered the LOQ). Values with decimal points will follow the same logic as above.
- The LOQ will be used to calculate descriptive statistics if the datum is reported in the form of “≤ x” or “≥ x” (where x is considered the LOQ).

COBAS[®] AmpliPrep/COBAS[®] TaqMan[®] HCV Quantitative Test, v2.0 will be used to determine HCV RNA results in this study. The lower limit of quantitation (LLOQ) of the assay is 15 IU/mL.

When the calculated HCV RNA value is within the linear range of the assay, then the result will be reported as the “<< numeric value>> IU/mL.” This result will be referred to in this document as the numeric result or as “≥ LLOQ detected” for categorical result.

When HCV RNA is not detected, the result is reported as “No HCV RNA detected” or “target not detected”. This result will be referred to in this document as “< LLOQ target not detected” or “< LLOQ TND.”

When the HCV RNA IU/mL is less than LLOQ of the assay, the result is reported as “< 15 IU/mL HCV RNA detected”. This result will be referred to in this document as “< LLOQ detected.”

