The overall category of HCV RNA < LLOQ includes “< LLOQ TND” and “< LLOQ detected.”

For numerical HCV RNA data, values below LLOQ will be set to the LLOQ 1 IU/mL (ie, 14 HCV RNA IU/mL). HCV RNA values returned as “No HCV RNA detected” will also be set to 14 IU/mL.

For selected analyses, HCV RNA data (IU/mL) will be transformed to the logarithmic (base 10) scale (\log_{10} IU/mL).

CCI
[Redacted]

CCI
[Redacted]

[Redacted]

[Redacted]

[Redacted]

[Redacted]

[Redacted]

[Redacted]

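### SAP 3.5.1 gives a missing HCV RNA result classified as below the LLOQ a numeric value above it (16 IU/mL), against the 14 IU/mL used for every other below-LLOQ result

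*SAP*

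**What the plan says.** SAP 3.5.1 handles missing HCV RNA in two steps. A missing result with below-LLOQ results on both sides is first given a category, either target not detected or detected but below the LLOQ. A number is then attached for the continuous analyses. This second step applies "when and only when a missing HCV RNA value is imputed as < LLOQ TND or < LLOQ detected", and in that case "the corresponding continuous value will be imputed to LLOQ + 1 IU/mL".

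The other rules for the same quantity are:

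- **Assay limit, SAP 3.6:** "The lower limit of quantitation (LLOQ) of the assay is 15 IU/mL".
- **Observed results below the limit, SAP 3.6:** "values below LLOQ will be set to the LLOQ 1 IU/mL (ie, 14 HCV RNA IU/mL"). The minus sign is missing from the text as quoted here, but the worked value of 14 settles the meaning.
- **Target not detected, SAP 3.6:** "HCV RNA values returned as “No HCV RNA detected” will also be set to 14 IU/mL".
- **Other non-PK continuous data, SAP 3.6:** "A value that is 1 unit less than the LOQ will be used to calculate descriptive statistics if the datum is reported in the form" that marks it as less than the limit. One unit above the limit is kept for greater-than results.
- **Protocol 8.2.2:** "HCV RNA values below the LLOQ for the assay will be set to the lower limit minus 1", for summaries of actual values and change from baseline by visit.

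SAP 6.2.2 feeds the values from 3.5.1 into the summaries and plots of log10 HCV RNA, absolute and change from baseline, through end of treatment. SAP 6.3, which lists departures from the protocol's efficacy analyses, names only the definition of the Full Analysis Set.

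**The concern.** The rule contradicts itself. It applies only to results that the SAP has just declared to be below 15 IU/mL, and it gives them a value above 15. On the SAP's own scale, a number in the assay's linear range is a quantifiable result: "This result will be referred to in this document as the numeric result or as “≥ LLOQ detected” for categorical result".

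It also conflicts with the neighbouring convention. A subject observed below the LLOQ enters the visit summary as 14. A subject whose missed sample is imputed to the same category enters the same column as 16. No reason is given for treating them differently.

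At stake is the internal consistency of a prespecified secondary endpoint. The continuous table could show a maximum above the LLOQ at a visit where the categorical table shows every subject below it. SAP 3.5.1 gives no worked value to expose the slip, so a programmer who follows it literally will code 16.

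**Working it through.** **Inputs**

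- LLOQ = 15 IU/mL (SAP 3.6, repeated in SAP 6.1.1).
- Value for an observed below-LLOQ result = 14 IU/mL (SAP 3.6).
- Value for an imputed below-LLOQ result = LLOQ + 1 (SAP 3.5.1).
- Planned cohort sizes: about 50 and about 30 (SAP 1.3).
- Number of bracketed missing samples per visit: not given. I assume 1 to 5.

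**Step 1: reproduce the stated figure.** LLOQ − 1 = 15 − 1 = 14 IU/mL. This matches the 14 printed in SAP 3.6 and the protocol's convention.

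**Step 2: apply SAP 3.5.1 as written.** LLOQ + 1 = 15 + 1 = 16 IU/mL. Since 16 is not below 15, the number disagrees with the category that triggered it.

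**Step 3: error per imputed value.**

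- log10(14) = 1.146, log10(15) = 1.176, log10(16) = 1.204.
- Difference between rules = log10(16/14) = 0.058 log10 IU/mL, a ratio of 1.143 or 2 IU/mL.
- The decline from baseline is understated by the same 0.058 for each such subject.

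**Step 4: effect on a visit mean.** With k imputed values among n subjects, the shift is k × 0.0580 / n.

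| n | k = 1 | k = 5 |
|---|---|---|
| 50 | 0.0012 | 0.0058 |
| 30 | 0.0019 | 0.0097 |

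The shift is 0.058 times the fraction imputed, so it is larger in a small genotype group but can never exceed 0.058.

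**Step 5: a fully suppressed visit with one imputed value.**

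- Under the minus rule, all values are 1.146 and the SD is 0.
- Under the plus rule, the maximum is 1.204, above log10(15) = 1.176.
- The SD becomes 0.0580/√n, which is 0.011 for n = 30 and 0.008 for n = 50.
- The median does not move.

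**Step 6: what is untouched.** SVR12 is defined by category (SAP 6.1.1). SVR4 and the percentage below LLOQ by visit use the categorical imputation (SAP 6.2.2). None of them uses the 16.

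**The case against.** The strongest objection is that nothing of substance turns on this. The trial tests no hypothesis, the affected analysis is descriptive, and the planned plots show mean ± SD and median with quartiles, so one value of 16 would not be visible in them. No subject is reclassified, because the category is set first and the number follows from it.

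The reach is also narrow. A bracketed success needs a below-LLOQ result before and after the gap. Eligibility requires quantifiable HCV RNA at Screening, so Week 2, the first on-treatment sample, can hardly ever qualify. The summary stops at end of treatment, which leaves missed samples at Weeks 4, 8 and 12. There may be none, although SAP 4.4 records that COVID-19 disrupted visits. All of this stands, and it limits the size of the problem.

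A second objection is scope. SAP 3.6 covers returned results and 3.5.1 covers missing ones, and the protocol sets no continuous value for a missing sample. It is true that the direct clash lies within the SAP, and that the protocol supplies the convention rather than a rule for this exact case. But both kinds of value enter the same summary under SAP 6.2.2, so the distinction does not remove the conflict.

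A third is that the plus might be a misread character, since a minus sign is missing from the sister sentence in SAP 3.6. This is unlikely. The visible losses are omissions, and plus signs appear correctly elsewhere, for example in the study-day formula in SAP 3.7.1.

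Nor does deliberate caution explain it. The SAP does not claim it, and caution is already applied where unbracketed missing results count as failures.

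**Conclusion.** The concern holds. SAP 3.5.1 assigns 16 IU/mL to results it has just classified as below 15 IU/mL, while SAP 3.6 assigns 14 to observed results in the same category and Protocol 8.2.2 uses the same minus-one convention. The difference is neither explained nor declared as a change, and a sign error is the most likely cause.

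The error is 0.058 log10 IU/mL per imputed value. If 1 to 5 values are imputed at a visit, it is about 0.001 to 0.010 log10 on a cohort mean. The number of such values is my assumption, and zero is possible. The visible symptom, a maximum above the LLOQ beside a table showing full suppression, needs a visit at which every observed value is below the limit. The conclusions on SVR12, SVR4 and virologic suppression are not affected. It should be corrected because a stated rule for a secondary endpoint gives the wrong number when followed.

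**What to change.** In SAP 3.5.1, change the plus to a minus and add the worked value, so that the imputed continuous value is LLOQ − 1 IU/mL, ie 14 IU/mL, in agreement with SAP 3.6. Check that the program line for the log10 HCV RNA summaries uses 14. If the SAP is already final, document the correction in the clinical study report, as SAP Section 1 provides.

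The cost is one character in the SAP and one program line. No other analysis changes, and I see no downside.
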